9.3.3 Covariates

Study covariates are listed here and will be measured at the index date or during the 12 months prior.

Variable	Description
Demographic and socioeconomic characteristics	
Age	Age as of index date in years rounded to the nearest whole number will be calculated based on the difference between the beneficiary's birth date and index date.
Age group	Age group will be a categorical variable for age defined as one of 65–74, 75–84, 85+.
Female	Female will be a binary indicator for whether the beneficiary was female as indicated on the enrollment record covering the index date.
Race	Race will be a categorical variable for the beneficiary's self-reported race/ethnicity taking the

BOEHRINGER INGELHEIM Group of Companies

NIS Protocol

BI Study Number 1199-0520

Page 18 of 35

c42255024-02

Proprietary confidential information © 2023 Boehringer Ingelheim International GmbH or one or more of its affiliated companies

Variable	Description
	categories Non-Hispanic White, Black or African-American, Other, Asian/Pacific Islander, Hispanic, American Indian/Alaska Native, and unknown race from the enrollment record covering the index date.
Census region	Census region will be a categorical variable defined by categorizing the beneficiary's state of residence into Census regions (Northeast, South, Midwest, West) from the enrollment record covering the index date.
Index year	Index year will be a categorical variable defined as the year of the index date and will take the values, 2014, 2015, 2016, 2017 or 2018.
Social deprivation index	Social deprivation index will be a continuous variable ranging between 0 and 100 representing the Social Deprivation Index for the beneficiary's residential ZIP Code as calculated by the Robert Graham Center. Social Deprivation Index "is a composite measure of seven demographic characteristics collected in the American Community Survey (ACS): percent living in poverty, percent with less than 12 years of education, percent single parent household, percent living in rented housing unit, percent living in overcrowded housing unit, percent of households without a car, and percent non-employed adults under 65 years of age." This version was calculated in 2015 using data from 2015 and updates the original version created by Butler et al. (2013). Higher values for the Social Deprivation Index indicate more social deprivation.
Clinical characteristics	
Combined comorbidity index	The combined comorbidity index will be a continuous comorbidity score ranging from 0 to 26 as measured from comorbidity diagnosis codes in any position on inpatient, outpatient and Carrier claims that occurred during the baseline period. The combined comorbidity score is based on research by Gagne et al. (2011) and Sun et al. (2017) to identify the conditions in the union of the two most-popular comorbidity indexes used in administrative claims data, the Charlson index and the Elixhauser index. For a sample of Medicare beneficiaries, Gagne et al. (2011) found that a subset of 20 conditions predicted mortality at 30, 60, 90 and 180 days, and 1 year more accurately than either of the two indexes

BOEHRINGER INGELHEIM Group of Companies

NIS Protocol

BI Study Number 1199-0520

Page 19 of 35

c42255024-02

Proprietary confidential information © 2023 Boehringer Ingelheim International GmbH or one or more of its affiliated companies

Variable	Description
	on their own. Moreover, unlike the Charlson and Elixhauser indexes, Gagne et al.'s (2011) combined index is not conditioned on inpatient hospital admission. The 20 conditions in Gagne et al.'s (2011) combined comorbidity index (with their weights in parentheses) include: 
 - Metastatic cancer (5), - Congestive heart failure (2), - Dementia (2), - Renal failure (2), - Weight loss (2), - Hemiplegia (1), - Alcohol abuse (1), - Any tumor (1), - Cardiac arrhythmias (1), - Chronic pulmonary disease (1), - Coagulopathy (1), - Complicated diabetes (1), - Deficiency anemia (1), - Fluid and electrolyte disorders (1), - Liver disease (1), - Peripheral vascular disease (1), - Psychosis (1), - Pulmonary circulation disorders (1), - HIV/AIDS (-1), and - Hypertension (-1).
Pulmonary hypertension	A binary indicator for whether the beneficiary had a diagnosis code for pulmonary hypertension on at least one inpatient, outpatient or Carrier claim that occurred during the baseline period.
Gastroesophageal reflux	A binary indicator for whether the beneficiary had a diagnosis code for gastroesophageal reflux disease on at least one inpatient, outpatient or Carrier claim that occurred during the baseline period.
Asthma	A binary indicator for whether the beneficiary had a diagnosis code for asthma on at least one inpatient, outpatient or Carrier claim that occurred during the baseline period.
Sleep apnea	A binary indicator for whether the beneficiary had a diagnosis code for obstructive sleep apnea on at least one inpatient, outpatient or Carrier claim that occurred during the baseline period.
Lung biopsy	A binary indicator for whether the beneficiary had a diagnosis or procedure code for a lung biopsy on at

BOEHRINGER INGELHEIM Group of Companies

NIS Protocol

BI Study Number 1199-0520

Page 20 of 35

c42255024-02

Proprietary confidential information © 2023 Boehringer Ingelheim International GmbH or one or more of its affiliated companies

Variable	Description
	least one inpatient, outpatient or Carrier claim that occurred during the baseline period.
HRCT scan	A binary indicator for whether the beneficiary had a procedure code for a high-resolution computerized tomography scan on at least one inpatient, outpatient or Carrier claim that occurred during the baseline period.
Oxygen	A binary indicator for whether the beneficiary had a diagnosis, procedure revenue center code for oxygen therapy or supplemental oxygen on at least one inpatient, outpatient, Carrier, skilled nursing facility, home health or durable medical equipment claim that occurred during the baseline period.
Pulmonary rehabilitation	A binary indicator for whether the beneficiary had a procedure or revenue center code for pulmonary rehabilitation services on at least one inpatient, outpatient, Carrier, skilled nursing facility, home health or durable medical equipment claim that occurred during the baseline period.
Ventilator use	A binary indicator for whether the beneficiary had a diagnosis or procedure code for ventilator use on at least one inpatient, outpatient or Carrier claim that occurred during the baseline period.
COPD	A binary indicator for whether the beneficiary had a diagnosis code for chronic obstructive pulmonary disease on at least one inpatient, outpatient or Carrier claim that occurred during the baseline period.
Hypoxia	A binary indicator for whether the beneficiary had a diagnosis code for hypoxia on at least one inpatient, outpatient or Carrier claim that occurred during the baseline period.
Pharmacy use and spending	
Medication count	The count of the number of unique outpatient prescription medications for which beneficiary has Part D claims during the baseline period
Total pharmacy spending	A continuous, non-negative variable representing the total amount paid by all parties for outpatient prescription medications as reported in Part D claims during the baseline period.
OOP pharmacy spending	A continuous, non-negative variable representing the total amount paid out-of-pocket by the beneficiary for outpatient prescription medications

Variable	Description
	as reported in Part D claims during the baseline period.
Inpatient hospitalization use and spending	
Any inpatient stay	A binary indicator for whether a beneficiary had at least one inpatient hospitalization for any cause during the baseline period.
Inpatient stay count	A count of the number of inpatient hospitalizations for any cause a beneficiary had during the baseline period.
Inpatient length of stay	A count of the number of days (length of stay) a beneficiary was hospitalized in an inpatient facility during the baseline period. Length of stay for each inpatient hospitalization claim will be calculated as the arithmetic difference between each claim's from and through dates.
Total inpatient spending	A continuous, non-negative variable representing the total amount paid by all parties for all inpatient hospitalizations (for any cause) as reported in inpatient facility claims during the baseline period. This is calculated as the sum of the Medicare payment amount, the Medicare per diem amount, the non-Medicare payer amount, and the patient OOP amount.
OOP inpatient spending	A continuous, non-negative variable representing the total amount paid out-of-pocket by the beneficiary for all inpatient hospitalizations (for any cause) as reported in inpatient facility claims during the baseline period.
Outpatient facility use and spending	
Any outpatient visit	A binary indicator for whether a beneficiary had at least one claim for services provided by an outpatient facility for any cause during the baseline period.
Outpatient visit count	A count of the number of unique dates with an outpatient facility for any cause claim a beneficiary had during the baseline period.
Total outpatient spending	A continuous, non-negative variable representing the total amount paid by all parties for outpatient facility claims during the baseline period. This is calculated as the sum of the Medicare payment amount, the blood deductible liability amount, the non-Medicare payer amount, and the patient OOP amount.

BOEHRINGER INGELHEIM Group of Companies

NIS Protocol

BI Study Number 1199-0520

Page 22 of 35

c42255024-02

Proprietary confidential information © 2023 Boehringer Ingelheim International GmbH or one or more of its affiliated companies

Variable	Description
OOP outpatient spending	A continuous, non-negative variable representing the total amount paid out-of-pocket by the beneficiary for services as reported in outpatient facility claims during the baseline period.
Home health use and spending	
Any home health	A binary indicator for whether a beneficiary had at least one claim for home health services during the baseline period.
Home health count	A count of the number of home health visits a beneficiary had during the baseline period, calculated by summing the total visit count on each claim across claims.
Total home health spending	A continuous, non-negative variable representing the total amount paid by all parties for home health claims during the baseline period. This is calculated as the sum of the Medicare payment amount, the blood deductible liability amount, the non-Medicare payer amount, and the patient OOP amount.
Part B spending	
Total Part B spending	A continuous, non-negative variable representing the total amount paid by all parties for Carrier and Durable Medical Equipment claims during the baseline period, calculated as the sum of the allowed amounts on each claim.
OOP Part B spending	A continuous, non-negative variable representing the total amount paid out-of-pocket by the beneficiary for Carrier and Durable Medical Equipment claims during the baseline period.
Total spending	
Total medical spending	A continuous non-negative variable representing the total amount paid by all parties for all medical services during the baseline period, including inpatient, outpatient, home health and Part B.
Total spending	A continuous non-negative variable representing the total amount paid by all parties for all medical and pharmacy claims during the baseline period and will be calculated as the sum of total pharmacy and total medical spending.
Other use	
Any ED visit	A binary indicator for whether a beneficiary had at least one emergency department visit during the baseline visit. Note that hospitals bill for emergency department visits on either the Inpatient or Outpatient facility claims, as described by

Variable	Description
	ResDAC here. Thus, emergency department visits will be identified in inpatient and outpatient facility claims via the presence of revenue center codes 0450-0459 and 0981.
ED visit count	A count of the number of unique dates with an emergency department visit that a beneficiary had during the baseline period.
Any pulmonology visit	A binary indicator for whether a beneficiary was treated by a specialist in pulmonary disease during the baseline period. Treatment by a pulmonologist will be identified by the presence of a pulmonary specialty code in inpatient, outpatient and Carrier claims.
Pulmonology visit count	A count of the number of unique dates with treatment by a specialist in pulmonary disease that a beneficiary had during the baseline period.
Pulmonology prescriber	A binary indicator for whether the clinician who prescribed the beneficiary's index nintedanib medication was a pulmonologist, as documented in the Part D Prescriber Characteristics file for the index nintedanib claim.

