9.2.2 Study population

- Inclusion criteria:
 - Newly initiated nintedanib during 10/01/2014 to 12/31/2018
 - Were at least 66 years old as of the date of their first nintedanib prescription claim (index date)
 - Qualified for Medicare based on age
 - Had at least 12 months of continuous enrollment in Medicare Parts A, B and D before (baseline period) and 12 months after the index date (follow-up period)
 - Had at least one inpatient or two outpatient claims (≥ 14 days apart) with a diagnosis code for IPF (ICD-10-CM: J84.112; ICD-9-CM: 516.31) during the baseline period
- Exclusion criteria:
 - Had any history of pirfenidone or nintedanib use during the baseline period
 - Had any history of lung transplant during the baseline, index date or follow-up periods
 - Had any claims for skilled nursing facility, long-term care facility or hospice during the baseline, index date or follow-up period
 - Had evidence (≥ 2 ICD-9-CM or ICD-10-CM diagnosis codes on different dates) during the baseline period of any of the following conditions: lung cancer, autoimmune, or connective tissue diseases (i.e., rheumatoid arthritis (RA), sarcoidosis, systemic lupus erythematosus (SLE), dermatopolymyositis, systemic sclerosis, Sjogren's, and mixed connective tissue disease (CTD)) during the baseline period (Appendix-1)
 - Had dual eligibility of Medicare and Medicaid.
 - Had history of using pirfenidone at the same time with nintedanib during follow-up

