9.6 DATA MANAGEMENT

Data manipulation and analysis will be conducted by [REDACTED]. Pursuant to requirements guiding participation in the [REDACTED] Innovator program, [REDACTED] staff will access the Medicare claims and enrollment data only through the [REDACTED]. As such, [REDACTED] will not directly possess any beneficiary-level [REDACTED] data, and the only data to be downloaded from the [REDACTED] will be summary-level statistics.

Data security will be assured along two dimensions. First, the data will reside only in [REDACTED] secure [REDACTED] environment. [REDACTED] staff have completed a rigorous identity verification process to gain access to the [REDACTED]. [REDACTED] prohibits any patient-level data from

Proprietary confidential information © 2023 Boehringer Ingelheim International GmbH or one or more of its affiliated companies being copied from the [REDACTED]; only aggregated data based on at least 11 patients is allowable. Second, only a limited set of patient identifiers will be present in the data, including residential ZIP Code and full dates of health insurance enrollment and claims and subject's birth and death dates. The unique patient ID used by [REDACTED] is a synthetic identifier, and no [REDACTED] study staff will have access to the linking file to real subject identifiers.

Additionally, study documents, including synopsis, protocol, and final results as well as publications, will be archived on the [REDACTED] Team site.

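### No baseline covariate uses the timing of events relative to nintedanib initiation, so adherence groups may differ in recent acute illness without the planned adjustment targeting or revealing it

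*Combined protocol and SAP*

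**What the plan says.** Section 9.3.3 fixes one covariate window: "Study covariates are listed here and will be measured at the index date or during the 12 months prior". The inpatient flag is typical: "A binary indicator for whether a beneficiary had at least one inpatient hospitalization for any cause during the baseline period". The ED count is "A count of the number of unique dates with an emergency department visit that a beneficiary had during the baseline period". Oxygen is a yes/no item over the same 12 months. No shorter sub-window is defined.

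Section 9.7.1 builds both sets of weights (inverse probability weights and marginal mean weights through stratification) from a multinomial logit on this roster. It then adds observed covariates to the outcome GLM and names no others. The planned descriptive comparison of groups also covers only these covariates.

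The dates needed for anything finer are available. Section 9.6 lists "full dates of health insurance enrollment and claims and subject's birth and death dates" among the fields present. Section 9.2.2 already requires dated IPF claims to be found, since a patient qualifies only if they "Had at least one inpatient or two outpatient claims" with an IPF code in the baseline period, the outpatient claims being at least 14 days apart.

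Section 9.9 concedes that IPF severity is absent from claims. It does not mention the recency of acute events or time since IPF was first coded.

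**The concern.** The exposure is the fill pattern over the 12 months after initiation, so the confounder that matters most is the patient's condition at initiation. A yearly total describes that only loosely. The any-stay flag and the oxygen flag give the same value for an event in the week before the index date as for one 11 months earlier.

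Double robustness does not help. It protects against misspecifying one of the two models, not against a variable missing from both. The groups could match exactly on every listed covariate and still differ in how recently patients had been in hospital. Nothing in the planned output would show it. If recent illness affects both later fills and later cost, part of that difference would be read as an effect of adherence.

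**Working it through.** The plan gives no power calculation and no figure on event timing, so there is no stated number to reproduce. The check has five steps.

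**1. The roster, row by row.** Clinical rows are 12-month yes/no items plus a weighted comorbidity score. Use and spending rows are 12-month flags, counts or sums. Some rows do use dates or the index claim, but none encodes distance from index:

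| Row | What it uses | Timing relative to index? |
|---|---|---|
| Inpatient length of stay | Claim from and through dates | No, duration only |
| Outpatient, ED and pulmonology counts | Unique dates | No, counts only |
| Pulmonology prescriber | The index claim | No event timing, specialty only |

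**2. Can a balanced flag hide a recency difference?** Let P be the 12-month prevalence of any stay, equal in both groups. Let s be the share of those patients whose stay was in the last month. The prevalence of a recent stay is r = P × s, and

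SMD = (r1 − r0) / √{[r0(1 − r0) + r1(1 − r1)] / 2}.

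P and s are assumptions; the documents give neither.

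| s0 vs s1 | P = 20% | P = 30% | P = 40% |
|---|---|---|---|
| 1/12 vs 1/12 | 0 | 0 | 0 |
| 1/12 vs 2/12 | 0.11 | 0.13 | 0.15 |
| 1/12 vs 3/12 | 0.19 | 0.23 | 0.27 |

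For P = 30% in the second row: r0 = 0.025, r1 = 0.050, and 0.025 / √{(0.024375 + 0.0475)/2} = 0.13. A perfectly balanced flag can therefore sit alongside a recency imbalance above 0.1, or alongside none.

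**3. Possible size on cost.** Let D be the extra cost of a recent stay over an older one, as a multiple of mean annual cost. Bias as a share of mean cost is P × (s1 − s0) × D. Assume P = 30%, a difference of 10 to 20 points and D = 0.5 to 1.0:

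- Low: 0.30 × 0.10 × 0.5 = 1.5%
- High: 0.30 × 0.20 × 1.0 = 6.0%
- Equal recency: 0%

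Over the unequal cases in the step 2 grid, the range is 0.20 × 1/12 × 0.5 = 0.8% to 0.40 × 2/12 × 1.0 = 6.7%.

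**4. Against precision.** Group sizes from sections 9.3.1 and 9.5 are 0.431 × 1,798 ≈ 775 highly adherent and 0.215 × 1,798 ≈ 387 rapid decliners. With an assumed cost CV of 1.5, the unweighted 95% half-width is 1.96 × 1.5 × √(1/775 + 1/387) = 1.96 × 1.5 × 0.0622 ≈ 18.3% of mean cost, so one standard error is about 9.3%. A 6% bias is 0.64 standard errors and would lower 95% coverage to about 90%. A 1.5% bias is 0.16 standard errors and leaves it at about 94.7%.

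**5. What look-back exists?** Data start on 10/01/2013. Possible look-back is 12 months for an index date of 10/01/2014 and about 63 months for 12/31/2018, but only 12 months of prior enrollment is required. Recency within 12 months can be derived for everyone. Time since first IPF code is uniform across patients only if cut at 12 months.

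**The case against.** The strongest reply has four parts.

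- **Existing covariates carry some of this information.** Part B spending includes durable medical equipment, so a patient on oxygen for 11 months would normally have more such claims than one who started last week. ED, pulmonology and home health counts may also pick up part of it. This stands: step 3 treats the whole recency difference as residual, so it leans high.
- **Eligibility removes some of the scenario.** Section 9.2.2 excludes patients with skilled nursing, long-term care or hospice claims at baseline, index or follow-up, and requires 12 months of enrollment after index. That plausibly removes many of the sickest recently discharged patients. It narrows the problem without closing it.
- **The prior study gives no support for the pathway.** Section 7 says baseline health care use was examined and names age, sex, race and ethnicity, and an additional medication as the principal correlates of lower adherence. Hospitalization is not named. Recency is not reported either, so this does not settle the point.
- **Missing severity is already disclosed in section 9.9.** True, but event timing can be derived from data the study holds, so it is not part of what claims cannot supply.

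A reader might infer more than the documents support. They do not show that the groups are in fact unbalanced on recency, since no group-level timing data are given. Nor do they show that the rapid-decliner contrast is pushed upward: a recent acute event could weaken adherence or reinforce it. It would also be wrong to say that every covariate is a 12-month total or that claim dates go unused, as the table in step 1 shows.

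**Conclusion.** The gap is real and narrow. No covariate in 9.3.3 uses timing relative to the index date, the weights come only from that roster, and the dates are held. A recency imbalance could therefore persist undetected in both models. Whether one exists, and in which direction, cannot be told from the documents.

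Under assumed inputs the effect on mean cost runs from zero to about 6%, against a half-width of about 18% that itself assumes a cost CV of 1.5 and ignores the variance added by weighting. This is a low-cost improvement to the adjustment set and does not by itself invalidate the analysis.

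Disease duration is a separate matter. A 12-month window cannot recover it: a long-standing patient first coded late in the window would look newly diagnosed. Only time since first observed code is available, and no size is claimed for it.

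**What to change.** In section 9.3.3, for both the propensity and outcome models:

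- **(a)** Add one indicator for any inpatient discharge within 90 days before index, alongside the existing any-stay flag and stay count. A patient with no stay, or with stays both inside and outside the 90 days, is then coded without ambiguity.
- **(b)** Replace the binary Oxygen flag with three levels: none, first baseline claim within 90 days of index, first baseline claim earlier. Keeping the old flag as well would be exactly collinear.
- **(c)** Add time from the first IPF-coded baseline claim to index, for example under 3, 3 to 6 and over 6 months. Label it as time since first observed code, truncated at 12 months, and not as disease duration.
- **(d)** Report weighted standardized differences across groups for these items.
- **(e)** Drop Total medical spending and Total spending from the models, because they are sums of other listed rows. Age group can stay.

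The cost is SAP wording and derivations from claims already held. Estimable coefficients rise by about four per equation: 1 for (a), 1 for (b) and 2 for (c). Over the four equations of the five-group multinomial logit that is 4 × 4 = 16. Dropping the two totals does not offset this, since they could not be estimated separately anyway. If the final report date of 15 May 2023 leaves no room to change the main models, the minimum is item (d) plus one sensitivity model that includes (a) to (c).

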9.2 SETTING

9.2.1 Study sites

The study will use 100% Medicare claims and enrollment data from the U.S. Medicare program on community-dwelling beneficiaries continuously enrolled in traditional, or fee-for-service, Medicare insurance coverage for inpatient hospital, skilled nursing and outpatient facility services (Part A), physician and other professional services (Part B), and outpatient prescription drugs (Part D).

The enrollment file contains monthly information on individuals' enrollment in each part of Medicare, demographic information, residential location (at the 5-digit ZIP Code level), and date of death.

Claims data are available for all medical services covered by the program and are organized into data files based on the nature and source of the claim. The Inpatient, Outpatient, and SNF files include institutional claims from hospitals for inpatient and outpatient services and from nursing homes for short-stay "skilled" admissions, respectively. The Carrier file includes fee-for-service claims submitted by professional providers, including physicians, physician assistants, clinical social workers, nurse practitioners. (Claims for some organizational providers, such as free-standing facilities are also found in the Carrier file. Examples include independent clinical laboratories, ambulance providers, free-standing ambulatory surgical centers, and free-standing radiology centers.) Separate files include claims for durable medical equipment, home health visits and hospice care.

Pharmacy Part D claims include complete prescription drug information, and all standardized prescription-level fields collected on a typical pharmacy claim (e.g., date of fill or refill, drug name and class, strength, quantity, and days' supply).

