Potential confounding by observed covariates will be addressed in two ways, thus leading to "doubly robust" estimates. The first way is to calculate two sets of observation-level weights that balance covariates across exposure categories: inverse probability of treatment weights (IPTWs) and weights derived from a marginal mean weighting through stratification (MMWS) procedure (Hong, 2012; Linden, 2014). To generate the weights, a multinomial logit model of nintedanib adherence trajectory group category will be estimated as a function of the covariate roster. Predicted probabilities (i.e., propensity scores) for each category will be generated from the model results and used to calculate both the IPTW and MMWS

Proprietary confidential information © 2023 Boehringer Ingelheim International GmbH or one or more of its affiliated companies weights. Because multiple exposure categories are to be compared, the weights will provide estimates of the average treatment effect (ATE) (and not the average treatment effect on the treated [ATT]).

The second way confounding will be addressed is through regression adjustment; that is, observed covariates will be added to the GLM specification. Combining weighting with regression adjustment yields a double robustness property that attenuates bias in the case when either the treatment model (i.e., the multinomial logit model of exposure category) or the outcome model (i.e., the GLM of the health care resource use or spending outcome) is misspecified (Linden et al., 2016).

To facilitate interpretability, the regression model results will be transformed back to the scale of the outcome variable. Average marginal effects and their 95% confidence intervals (CIs) will be calculated using the delta method. Data preparation will be performed using SAS 9.4 (██████████) and data analysis will be conducted using Stata 17 (██████████).

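### The covariate roster has no dedicated measure of frailty or functional limitation, although the baseline claims already held would allow one, so frailty is controlled only in part

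*Combined protocol and SAP*

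**What the plan says.** Section 9.3.3 opens with "Study covariates are listed here and will be measured at the index date or during the 12 months prior" and then lists every covariate. Section 9.7.1 builds the weights from that list: "a multinomial logit model of nintedanib adherence trajectory group category will be estimated as a function of the covariate roster". The observed covariates are then also added to the outcome GLM, so one list serves both halves of the doubly robust estimator.

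Section 9.2.1 describes the files held. Besides inpatient, outpatient and Carrier claims, "Separate files include claims for durable medical equipment, home health visits and hospice care". DME claims are already read for three covariates in section 9.3.3: oxygen, pulmonary rehabilitation, and total Part B spending. In the last of these, DME dollars are pooled with Carrier dollars and carry no item type.

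Section 9.9 concedes that claims omit determinants of cost and use that may be correlated with adherence. It gives IPF severity as the example. Frailty is not named.

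**The concern.** In a cohort aged 66 or older, frailty could plausibly lead both to falling nintedanib fills and to later hospital use and cost. If it differs between trajectory groups after weighting, part of the adjusted contrast reflects frailty and not adherence. The likely direction is the one the study expects, lower adherence with higher cost, so an expected result would not expose the problem.

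Double robustness protects against misspecifying one of the two models. It gives no protection against a confounder missing from both. The objectives in section 8 speak of association, but section 9.7.1 targets an average treatment effect and section 7 expects the findings to inform ways to improve adherence. Control of confounding is therefore a fair standard.

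Frailty differs from IPF severity in one practical respect: diagnosis, home health and DME claims allow it to be partly measured.

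**Working it through.** **Step 1. What the roster holds.** Section 9.3.3 has no frailty index, no wheelchair, walker or hospital-bed indicator, and no falls or functional-status item. The covariates that carry part of the signal are:

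- age and medication count;
- a comorbidity score that includes dementia (weight 2), weight loss (2) and hemiplegia (1), entered as one summed number;
- oxygen, hypoxia, ventilator use and pulmonary rehabilitation;
- home health use, inpatient stays and days, and ED visits;
- baseline spending by category and in total.

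Section 9.2.2 also excludes patients with skilled nursing, long-term care or hospice claims, and dual eligibles. This lowers the amount of frailty in the cohort. It does not balance what remains across the five groups.

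**Step 2. Group sizes and precision.** Section 9.5 carries 1,798 patients over from the prior study and gives no power calculation, so there is no derived figure to reproduce. Applying the shares in section 9.3.1 (43.1, 11.9, 10.4, 13.2 and 21.5%) gives 775, 214, 187, 237 and 387. These sum to 1,800 because the shares sum to 100.1%, which agrees with 1,798 within rounding.

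For rapid decliners versus highly adherent, in SD units and ignoring both the weights and any precision gained from covariates:

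- SE = √(1/775 + 1/387) = 0.0622
- 95% half-width = 1.96 × 0.0622 = 0.122 SD

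If the cost SD equals the mean (assumed), this is about 12% of the mean. If the SD is 1.5 times the mean, it is 0.122 × 1.5, or about 18%.

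**Step 3. A ceiling with no adjustment at all.** For a binary confounder with prevalence p1 and p0 in the two groups and cost ratio R, the relative bias is [1 + p1(R − 1)] / [1 + p0(R − 1)] − 1. Assume p0 = 0.15.

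- p1 = 0.25, R = 1.3: 1.075/1.045 − 1 = 2.9%
- p1 = 0.30, R = 2.0: 1.30/1.15 − 1 = 13.0%

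This is not the planned analysis, which adjusts for the covariates in step 1.

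**Step 4. Bias against precision.** Let D be the difference in frailty prevalence between the two groups, G the frail versus non-frail cost gap in SD units, and r the share of bias left after the listed covariates. All three are assumed. Then b = r × D × G. With no true effect, the chance that the 95% CI excludes zero is 1 − Φ(1.96 − b/SE) + Φ(−1.96 − b/SE).

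| D | G | r | b (SD) | b / half-width | CI excludes zero |
|---|---|---|---|---|---|
| 5 points | 0.5 | 1 | 0.025 | 0.20 | 6.9% |
| 10 points | 0.5 | 1 | 0.05 | 0.41 | 12.7% |
| 10 points | 0.5 | 0.5 | 0.025 | 0.20 | 6.9% |
| 10 points | 1.0 | 1 | 0.10 | 0.82 | 36.2% |
| 10 points | 1.0 | 0.5 | 0.05 | 0.41 | 12.7% |
| 20 points | 1.0 | 1 | 0.20 | 1.64 | 89.5% |

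The last row is extreme. With a cost ratio of 1.3 to 1.8 and an SD of 1 to 1.5 times the mean, G is roughly 0.3/1.5 = 0.2 to 0.8/1 = 0.8.

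**Step 5. Residual bias after adjustment.** Simulation with a log-link cost model, cost ratio 1.3 to 1.8 and exposure odds ratio 1.5 to 2.0 (all assumed) gives the following.

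- Adjusting only for age, comorbidity and home health (correlation 0.45 to 0.6 with latent frailty; frailty differing by 9 to 14 points) leaves 1.6% to 6.5%.
- With frailty at 18% and three proxies at correlation 0.5, about 1% to 5% remains. Adding five weaker proxies (correlation 0.35) and baseline spending lowers this to about 0.2% to 2.7%, with Monte Carlo error near 0.5 points.

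The second setting with baseline spending is closer to the plan. Its low range comes almost wholly from baseline spending, and so depends on how closely that spending is assumed to track frailty. The documents give nothing on that.

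**The case against.** The strongest reply is that the plan already does much of this work. The listed covariates are numerous, baseline spending is among them, and the exclusions remove much of the severe frailty. In the prior study summarised in section 7, demographics, comorbidities and health care use were all examined, and the principal factors for lower adherence were older age, female sex, race and ethnicity, and an additional medication. Comorbidity and health care use, where frailty would be expected to show, are not among them. Age and medication count are already adjusted for, so their appearance there is not evidence of residual confounding. Section 9.9 gives IPF severity only as an example of an unmeasured determinant. All of this stands, and it limits the size of the concern. It does not put a measure of physical function into either model.

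A reader might go further in three ways that the documents do not support:

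- **Frail patients shown to stop early and cost more.** Nothing in the documents demonstrates this. It is plausible only.
- **DME claims left unused.** They already feed oxygen, pulmonary rehabilitation and Part B spending. What is missing is an item-level functional use.
- **Strength on the index claim as a remedy.** Section 9.2.1 lists the field ("date of fill or refill, drug name and class, strength, quantity, and days' supply"), but nothing ties it to frailty. It is an attribute of the dispensed treatment and does not belong in this point.

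**Conclusion.** The point holds as a cheap improvement. The roster has no dedicated frailty or functional-limitation measure, one can be derived from baseline claims already held, and section 9.9 does not name frailty. The existing covariates and exclusions control it in part, so some residual confounding toward higher cost with lower adherence is plausible.

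Its size cannot be fixed from the documents, which give no frailty prevalence, cost ratio or cost SD. Under the inputs assumed above it is probably a few percent of cost or less, below the 12% to 18% half-width for the largest contrast with the reference group. The 2.9% to 13.0% range in step 3 should not be read as the expected bias, since it assumes no adjustment. A dollar figure would need a mean cost that the documents do not supply.

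**What to change.** Add to section 9.3.3, and so to both the multinomial logit and each outcome model, one prespecified baseline variable: either a claims-based frailty score, or an indicator for at least one baseline DME claim for a functional aid (wheelchair, walker, hospital bed or similar). Report its balance across the five groups after weighting. Name frailty in section 9.9 as only partly measured.

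The cost is a code list. A five-category logit has four equations, so one binary indicator or one continuous score adds four coefficients there, plus one in a single-part outcome model or two in a two-part model. The loss of precision should be small, and no new data are needed.
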